9.2 DISCONTINUED SUBJECTS

Discontinued subjects are those who voluntarily discontinue participation, who are withdrawn for safety reasons or who have missed a sufficient number of study visits, procedures or test article doses, as defined below, to be ineligible for further participation.

All subjects who discontinue the study prior to completing the regularly scheduled visits should complete the End of Treatment Assessment or Early Discontinuation Visit 14.

Any changes in medical health and/or the use of concomitant medications will be captured. If any SAE, target ulcer AE, or DevD were observed since the previous visit, they must be recorded (refer to Section 12, *Adverse Events*, for instructions on reporting and evaluation

procedures). All females of child-bearing potential must also undergo a urine pregnancy test upon exiting the study. Finally, if appropriate, the Investigator will also advise the subject of subsequent therapy and/or procedures necessary for their medical condition.

During the course of the study, the subject must be discontinued from study treatment in the case of any of the following:

- An infection of the target ulcer occurs and does not respond as expected to appropriate conventional treatment after 2 weeks of therapy
- Progressive disease defined by an increase of $\geq 75\%$ in the ulcer surface area at any time during the treatment phase using the measurement from Run-in Visit 2 as the baseline target ulcer measurement. The increase is calculated as follows:

$$\left[\left(\frac{Area_{V_n} - Area_{RV2}}{Area_{RV2}} \right) \times 100 \right] \geq 75$$

- Persistence of an SAE, device –related AE or abnormal laboratory value that in the opinion of the Investigator places the subject at risk should they continue in the study
- Subject misses > 2 weekly study visits during the treatment period.
- Subject misses 14 consecutive days of therapy or standard care treatment during the treatment period
- Subject misses 21 cumulative days of therapy during the treatment period

Subjects may be discontinued from the study at any time if, in the opinion of the Investigator, their continued participation in the study poses a risk to the subject. Additionally, subjects may be discontinued from the study for the following reasons:

- Adverse device effects
- Lost to follow-up
- Subject decision unrelated to an adverse device effects
- Noncompliance (e.g., did not follow instructions, took disallowed medications)
- Other

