9.4 STUDY METHODS AND MEASUREMENTS

For purposes of derivation of endpoints and subsequent analysis, study treatment refers to either PICO or tNPWT. Four individual negative pressure wound therapy devices are available for use during the study; the data for the study endpoints collected for each of these individual devices will be pooled to constitute the tNPWT treatment arm.

Primary Endpoint

The primary endpoint for this study is the percentage change in target ulcer area over the 12-week treatment period. Target ulcer area is defined as surface area as measured by the ARANZ Silhouette Device (18.2) at each study visit by the Investigator. The percentage change in target ulcer area over the 12-week treatment period is then defined as:

CONFIDENTIAL DOCUMENT
This document contains confidential information, which is the property of Smith & Nephew, Inc. Do not copy, disclose, or circulate without written authorization from the appropriate Smith & Nephew personnel

$$\text{Percentage change in target ulcer area} = \left(\left(\frac{\text{Area}_{SV13} - \text{Area}_{SV1}}{\text{Area}_{SV1}} \right) \times 100 \right)$$

In cases where the target ulcer area is closed in the opinion of the Investigator (regardless of 1-week confirmation), the ulcer area will be imputed as 0 cm², resulting in a percentage change in target ulcer area of 100%. In circumstances where the ulcer area is missing at the Study Visit 13 for subjects that have not withdrawn prematurely due to closure, the last observation carried forward (LOCF) method will be used.

Key Secondary Endpoints

The key secondary endpoints are the percentage change in the target ulcer dimensions not assessed as part of the primary endpoint, namely depth and volume. As defined for the primary endpoint, ulcer depth and volume will be measured by the ARANZ Silhouette Device at each visit by the Investigator, and the percentage change in depth and volume over the 12-week treatment period will then be defined as per the formula above replacing the area measurements with the corresponding depth and volume respectively.

Secondary Endpoints

The secondary endpoints are as follows:

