10.3 EFFICACY ANALYSIS

10.3.1 Primary Efficacy

The primary endpoint of the study is the percentage change in target ulcer area over the 12-week treatment period and will be analyzed as follows. An initial linear regression model will contain covariates for treatment, center, wound type, baseline (defined as Study Visit 1) target ulcer area and duration of target ulcer. For purposes of the primary analysis, any centers with less than 10 subjects will be pooled. A forward selection procedure will be used for the addition of other baseline covariates with an F-value to attain a significance level of 0.1. Further baseline covariates to be assessed as part of this procedure include: subject age, body mass index, baseline ulcer depth, ABI and baseline level of exudate. The resulting primary analysis presented will correspond to the final model from the forward selection procedure. The results for the initial model will also be presented. For each of the effects in the initial and final model, the p-value, parameter estimate and corresponding 95.4% confidence interval will be presented.

Secondary subgroup analyses may be conducted as a result of the covariate analyses. Additionally, treatment will be fitted on its own in a further linear regression model. The potential for interactions, particularly treatment by center interactions will be examined by fitting the required interaction terms in addition to those effects in the final linear regression model from the forward selection procedure.

Non-inferiority will be concluded in each case if the upper bound of the 95.4% confidence interval for the parameter estimate relating to treatment covariate (coded as tNPWT – PICO) is less than ($<$) 12.5 which relates to the desired one-sided test at the 2.5% significance level after adjusting for the interim analysis.

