11. SAMPLE SIZE JUSTIFICATION

The study is intended to test for non-inferiority in the percentage change in target ulcer area between PICO and tNPWT over a 12-week treatment period. During a review of five previous studies with venous leg ulcer and diabetic foot ulcer, with treatment of PICO or tNPWT, the mean percentage change in ulcer area was found to be approximately between 47-62%, in cases where it was considered an appropriate measure, the standard deviation ranged approximately between 21-24.5%. Using a non-inferiority margin of 12.5%, a sample size of 128 subjects will provide 80% statistical power at the (cumulative) 0.025 one-sided significance level assuming a weighted average mean healing of 60% with a worst case standard deviation of 24.5%. To allow for a 20% drop out rate throughout the 12-week treatment period, a total of approximately 160 subjects (80 per treatment) will be randomized.

The sample size randomized will include a minimum of 100 VLU to allow for a minimum of 70% power for VLU-only analysis using the above assumptions.

An interim analysis (built into the sample size) of key variables will take place after approximately 50% of target recruitment (80 subjects completed) with the stipulation that the interim will contain at least 40 VLU and 20 DFU. The interim analysis will contain a check for efficacy with an alpha spend of 0.002. A non-binding look for futility will also be performed at the same time point. The Lan and DeMets (1983) “Pocock” spending function will be used²⁴. If the efficacy boundary of 2.963, using the Z scale is exceeded ($Z > 2.963$) a recommendation will be made to terminate the trial on the basis of efficacy. Alternatively, if the futility bound of 0.559 using the Z scale is crossed ($Z < 0.559$) it will be recommended to terminate the trial prematurely due to lack of efficacy (futility). Further details regarding the stopping criteria, including the corresponding values on the p-value scale to be used in circumstances where distributional assumptions do not hold, can be found in the SAP.

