2.3 EFFICACY/SAFETY MEASURES AND ENDPOINTS

2.3.1 PRIMARY ENDPOINT

The primary endpoint for this study is the percentage change in target ulcer area over the 12-week treatment period. Target ulcer area is defined as surface area as measured by the ARANZ Silhouette Device at each study visit by the Investigator.

The percentage change in target ulcer area over the 12-week treatment period is

Document Number: 1004313

Document Part: 000

Document Version: 06

Document Status: Released

then derived using the baseline area and the area recorded at Study Visit 13. In cases where the target ulcer area is closed in the opinion of the Investigator (regardless of 1-week confirmation), the ulcer area will be imputed as 0 cm². In circumstances where the ulcer area is missing at the Study Visit 13 for subjects that have not withdrawn prematurely due to closure, the last observation carried forward (LOCF) method will be used.

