3. STATISTICAL CONSIDERATIONS

3.1 DETERMINATION OF SAMPLE SIZE

The study is intended to test for non-inferiority in the percentage change in target ulcer area between PICO and tNPWT over a 12-week treatment period. During a review of five previous studies with venous leg ulcer and diabetic foot ulcer, with treatment of PICO or tNPWT, the mean percentage change in ulcer area was found to be approximately between 47-62%, in cases where it was considered an appropriate measure, the standard deviation ranged approximately between 21-24.5%. Using a non-inferiority margin of 12.5%, a sample size of 128 subjects will provide 80% statistical power at the (cumulative) 0.025 one-sided significance level assuming a weighted average mean healing of 60% with a worst case standard deviation of 24.5%. This was calculated using EAST 6. To allow for a 20% drop out rate throughout the 12-week treatment period, a total of approximately 160 subjects (80 per treatment) will be randomized.

The sample size randomized will include a minimum of 100 VLU to allow for a minimum of 70% power for VLU-only analysis using the above assumptions.

An interim analysis (built into the sample size) of key variables will take place after approximately 50% of target recruitment (80 subjects completed) with the stipulation that the interim will contain at least 40 VLU and 20 DFU. A recommendation may be made at this point to stop the trial prematurely due to efficacy or futility.

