15. The change in target ulcer area during the screening period will be derived as (change in depth and volume will be derived using the same method):

$$Area_{Run-In\ 2} - Area_{Run-In\ 1}$$

16. The percentage change in target ulcer area during the screening period will be derived as (percentage change in depth and volume will be derived using the same method):

$$\left(\frac{Area_{Run-In\ 2} - Area_{Run-In\ 1}}{Area_{Run-In\ 1}} \right) \times 100$$

17. Target ulcer area is defined as surface area as measured by the ARANZ Silhouette Device at each study visit by the Investigator. For each study visit, the change in target ulcer area will be derived as (change in depth and volume will be derived using the same method):

$$\text{Change in target ulcer area at Study Visit } n = Area_{SVn} - Area_{SV1}$$

18. For each study visit, the percentage change in target ulcer area will be derived as (percentage change in depth and volume will be derived using the same method):

$$\text{Percentage change in target ulcer area at Study Visit } n = \left(\frac{Area_{SVn} - Area_{SV1}}{Area_{SV1}} \right) \times 100$$

For purposes of the primary analysis, the percentage change in target ulcer area will be derived as using LOCF within the 12-week treatment period. The percentage change in depth and volume will be derived using the same method.

19. The time to achieve confirmed ulcer closure in days will be derived as follows:
- For those subjects that achieve confirmed closure (derived variable 20):
Date of Study Visit where closure is first recorded – Date of Randomization
 - For those subjects that achieve closure but do not achieve confirmation (derived variable 20):
Date of Study Visit where closure is first recorded – Date of Randomization
 - For those subjects that do not achieve closure during the 12-week treatment period or withdraw early, the time to achieve confirmed ulcer closure will be defined as either: Date of last study visit attended – Date of Randomization;
Or 84 days, whichever occurs earlier.

20. Whether confirmed ulcer closure was achieved will be derived as follows:

- Ulcer Closed/Ready for surgical closure=Yes at last attended Study Visit i, Ulcer Closed=Yes at Follow up assessment (Visit 14). Confirmed Closure = Yes
- Ulcer Closed/Ready for surgical closure =Yes at last attended Study Visit i, Ulcer Closed=No at Follow up assessment (Visit 14). Confirmed Closure = No

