4.9 Primary Variable

The primary objective of the study is to compare PICO against ActiV.A.C.® in terms of the percentage change in the target ulcer area, over the 12-week treatment period.

Primary Analysis

An initial linear regression model will contain covariates for treatment, center, wound type, baseline (defined as Run-In Visit 2/Study Visit 1) target ulcer area and duration of target ulcer. For purposes of the primary analysis, any centers with less than 10 subjects will be pooled. A forward selection procedure will be used for the addition of other baseline covariates with an F-value to attain a significance level of 0.1. Further baseline covariates to be assessed as part of this procedure include: subject age, body mass index, baseline ulcer depth, ABI and baseline level of exudate. The resulting primary analysis presented will correspond to the final model from the forward selection procedure. The results for the initial model will also be presented. For each of the effects in the initial and final model, the p-value, parameter estimate and corresponding 95.4% confidence interval will be presented.

Non-inferiority will be concluded if the upper bound of the 95.4% confidence interval for the parameter estimate relating to treatment covariate (coded as ActiV.A.C.® – PICO) is less than ($<$) 12.5 which relates to the desired one-sided test at the 2.5% significance level after adjusting for the interim analysis.

If distributional and model assumptions relating to the above analysis do not hold, a permutation test will be used as a non-parametric non-inferiority analysis. The sampling distribution of the test statistic will be estimated by re-randomization of treatments to each of the study subjects. At a minimum the completed re-randomization process will be repeated 2000 times. However, if 2000 replicates are found to be insufficient for the random variation in results of successive repeats to be reduced to an acceptable level, the number of replicates will be increased until such a point as consistent results are observed between successive repeats of the permutation tests up to a maximum of 10,000 replicates.

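### The primary endpoint formula makes healing negative, but the non-inferiority rule needs healing to be positive; applied as written, the test asks whether tNPWT is non-inferior to PICO

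*Protocol*

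**What the plan says.** **Formula.** Protocol 9.4 defines the primary endpoint as (Area at Study Visit 13 - Area at Study Visit 1) / Area at Study Visit 1 x 100. SAP 4.3 item 18 has the same form: "For each study visit, the percentage change in target ulcer area will be derived as" (Area_SVn - Area_SV1) / Area_SV1 x 100. It then applies this to the primary analysis with LOCF and no change of sign.

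**Closure.** Protocol 9.4 imputes 0 cm² for a closed ulcer, "resulting in a percentage change in target ulcer area of 100" per cent. SAP 2.3.1 says only that "the ulcer area will be imputed as 0" cm²; neither it nor SAP 2.3.5 repeats the 100% statement.

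**Decision rule.** Protocol 10.3.1 concludes non-inferiority if the "upper bound of the 95.4% confidence interval for the parameter estimate relating to treatment covariate (coded as tNPWT – PICO) is less than" 12.5. SAP 4.9 applies the same limit to the "parameter estimate relating to treatment covariate (coded as ActiV.A.C.® – PICO) is less than" 12.5.

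**Sample size.** Protocol 11 reports that "the mean percentage change in ulcer area was found to be approximately between 47-62" per cent in earlier studies. SAP 3.1 gives the same range and plans on 128 completers, "assuming a weighted average mean healing of 60% with a worst case standard deviation of 24.5" per cent.

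**Dependent steps.** The interim rule (Protocol 11, SAP 3.3) recommends stopping for efficacy at Z > 2.963 and for futility at Z < 0.559, without a formula for Z. The permutation test (Protocol 10.3.1, SAP 4.9) shifts re-assigned subjects by the margin, up or down, without naming the arm for each direction. Depth and volume repeat the primary analysis (Protocol 10.3.2, SAP 4.10).

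**The concern.** The formula and the closure value cannot both be right: an ulcer imputed as 0 cm² scores -100, not +100. Three elements take healing as positive (the closure value, the planning means and the direction of the rule). Only the formula takes it as negative, but the formula is what the SAP tells the programmer to derive.

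The rule limits how far tNPWT may exceed PICO. If larger values mean more healing, that caps PICO's shortfall, as intended. If larger values mean less healing, it caps tNPWT's shortfall and leaves PICO's unlimited. Item 18 followed by SAP 4.9, programmed as written, therefore tests whether tNPWT is non-inferior to PICO. A worse PICO would tend to be declared non-inferior and a better one would tend to fail. The two key secondary endpoints inherit the same reversal.

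**Working it through.** **Inputs.** Margin 12.5, SD 24.5, 128 completers, one-sided cumulative level 0.025 (Protocol 11, SAP 3.1); 1:1 allocation, so 64 per arm; 95.4% interval (Protocol 10.3.1, SAP 4.9); interim bounds 2.963 and 0.559 after 80 completers (Protocol 11, SAP 3.3).

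**The plan's sample size.** A fixed design needs 61 per arm, 122 in total. A two-look calculation with the stated bounds, information fraction 0.5 and a final bound of 1.969 (solved for cumulative alpha 0.025) gives 80.2% power at 128 when the futility bound is applied, and needs 127.4, that is 128, for 80%. Dropout: 128 / 0.8 = 160. The plan's figures are reproduced. The calculation assumes equal arms, where both signs give the same answer, so it cannot reveal the error.

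**Closure under the formula.** (0 - A)/A x 100 = -100.

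**One worked case.** SE = 24.5 x sqrt(2/64) = 4.331. The 95.4% half-width is 1.995 x 4.331 = 8.64. Take true reductions of 60 for tNPWT and 47.5 for PICO.
- Literal formula: -60 - (-47.5) = -12.5; expected upper limit -12.5 + 8.64 = -3.86, below 12.5, so PICO passes.
- Reduction scale: 60 - 47.5 = +12.5; expected upper limit 12.5 + 8.64 = 21.14, so PICO fails.

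**Probability of concluding non-inferiority, final look only.** Let d = PICO - tNPWT in percentage reduction.
- Reduction scale: P = Phi((12.5 + d)/4.331 - 1.995)
- Literal formula: P = Phi((12.5 - d)/4.331 - 1.995)

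| True position of PICO | Literal formula | Reduction scale |
|---|---|---|
| 12.5 points worse (d = -12.5) | 99.99% | 2.3% |
| 6 points worse (d = -6) | 98.9% | 31.0% |
| Equal (d = 0) | 81.3% | 81.3% |
| 12.5 points better (d = +12.5) | 2.3% | 99.99% |

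A simulation of 40,000 trials per scenario, using t-based limits, agrees: 99.99% against 2.2% when PICO is 12.5 points worse.

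**Interim look.** The plan gives no formula for Z, so assume Z = (12.5 - [tNPWT - PICO])/SE on whichever scale is used.
- 40 per arm (80 completers), SE = 24.5 x sqrt(2/40) = 5.478. If PICO is 12.5 points worse, the literal mean of Z is 25/5.478 = 4.563 and P(Z > 2.963) = Phi(1.600) = 94.5%. On the reduction scale the mean is 0 and the probability is 0.15%.
- 32 per arm (half of 64), SE = 6.125. The literal mean is 25/6.125 = 4.082, giving Phi(1.119) = 86.8%.
- If PICO is 12.5 points better, the literal mean is 0 and P(Z < 0.559) = 71%, whatever the interim size.

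A simulation of both looks (2,000,000 trials, 40 then 64 per arm, PICO 12.5 points worse) gives an overall pass rate of 99.99% literal against 2.3% on the reduction scale.

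**The case against.** The strongest reply is that the intended direction can be recovered. Closure is called 100%, the planning means are positive, and high Z is labelled efficacy. SAP 3.1 also uses the positive scale, so the SAP contradicts itself rather than consistently specifying a reversed test. This stands: the reversal occurs only if item 18 is programmed literally.

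It is also less than certain that the formula is the error. Protocol 9.1.2 pairs a signed run-in formula with a threshold worded as a decrease of positive size. On that usage, 100% and 47-62% could be loose magnitudes and the contrast would be the mistake. That affects which sentence to correct, not whether the sentences conflict.

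Protocol 9.2 uses the same form of formula for growth of at least 75% "in the ulcer surface area at any time during the treatment phase". It is a discontinuation rule and does not define the endpoint; it shows only that the signed form is used literally elsewhere.

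The permutation shift and interim Z are not independent defects. Once the scale is fixed, the shift follows from the stated null and the coding of the contrast, and the favourable direction of Z is already given. Still, neither is written out.

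Finally, a reversed result might be noticed. SAP 4.9 summarises baseline area, final area and absolute change by arm, and the closure analyses in SAP 4.10 do not depend on this sign. That is a safeguard against publishing the error, not a definition. The trial is open-label and analysed by the sponsor's own department, so the direction of the primary test should not be settled after the data are seen.

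**Conclusion.** The concern holds: the definition is wrong as written and must be corrected. The formula contradicts the closure value, the sample-size scale and the non-inferiority rule, and neither document resolves the conflict. Percentage reduction is the probable intent. On that scale the rule works as designed: 2.3% passes when PICO is exactly 12.5 points worse and 81.3% when the arms are equal.

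Applied literally, the pass rates for a PICO 12.5 points worse and one 12.5 points better change places. These figures assume normal outcomes with SD 24.5 and 64 per arm at the final look. The interim figure (94.5%, or 86.8% with 32 per arm) also rests on an assumed form of Z.

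**What to change.** Choose one scale and state it in Protocol 9.4 and SAP 4.3 item 18.

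- **Preferred:** define the analysed endpoint as percentage reduction, (Area_SV1 - Area_SV13)/Area_SV1 x 100, with closure = +100, and keep the rule in Protocol 10.3.1 and SAP 4.9.
- **Alternative:** keep the signed formula, correct closure to -100, and require the upper limit of PICO - tNPWT to be below 12.5. This is the same test.

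Then carry the choice through:
- **Depth and volume** (Protocol 10.3.2, SAP 4.10): same scale and contrast.
- **Interim** (Protocol 11, SAP 3.3): write the statistic out, for example Z = (12.5 - [tNPWT - PICO in percentage reduction])/SE.
- **Permutation test** (Protocol 10.3.1, SAP 4.9): on the reduction scale, subtract 12.5 for a tNPWT subject re-assigned to PICO and add 12.5 for a PICO subject re-assigned to tNPWT. The signs swap if the signed formula is kept.

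The cost is wording in the protocol and SAP. Sample size, margin and data collection do not change.

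### LOCF is the only method for a missing Visit 13 value of an open ulcer, with no sensitivity analysis, which weakens the Full Analysis Set as a check on the Per Protocol result

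*Protocol*

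**What the plan says.** Protocol 9.4 (Primary Endpoint) sets the area of a closed ulcer to 0 cm². For a missing Visit 13 area in a subject who did not leave because of closure, "the last observation carried forward (LOCF) method will be used". SAP 2.3.1, 2.3.5 and 4.3 (item 18) repeat the rule, and SAP 2.3.5 extends it to depth and volume. Protocol 10.2 only refers to the SAP.

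The worst-case and best-case derivations in SAP 2.3.5 and 4.10 cover confirmed closure and time to closure. The permutation test in SAP 4.9 deals with distributional assumptions, not missing values. Area, depth and volume therefore have no missing-data sensitivity analysis.

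Missing values are expected. Protocol 11 inflates the sample size "To allow for a 20% drop out rate throughout the 12-week treatment period", and Protocol 9.2.1 does not replace subjects lost after randomization.

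Under Protocol 10.3.1 the primary test is in the Per Protocol Population and is repeated in the FAS. Differences in conclusions are to be investigated, and superiority is considered only if both sets show non-inferiority. Protocol 10.1 removes from Per Protocol those who stop treatment before about week 9 without closure. The FAS keeps anyone treated who has one post-baseline follow-up.

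**The concern.** LOCF gives a drop-out the area from an earlier week. If one arm heals more slowly, the arms have separated less by then than at week 12, so the carried values understate the final difference. In a superiority trial that is usually conservative. In a non-inferiority trial, with similar drop-out in both arms, it moves the estimate away from the margin and towards the claim. LOCF also treats the carried value as if it had been observed.

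The FAS is where this matters, because it is the only efficacy set that keeps the early discontinuers with open ulcers. The plan uses it to test whether the Per Protocol conclusion survives their inclusion. If their values are filled in by a method that tends to shrink a deficit, agreement between the two sets is less reassuring than it looks.

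**Working it through.** **Inputs from the documents**

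- Protocol 11: "Using a non-inferiority margin of 12.5%, a sample size of 128 subjects"; "80% statistical power at the (cumulative) 0.025 one-sided significance level"; "weighted average mean healing of 60" percent; "worst case standard deviation of 24.5" percent (review range 21 to 24.5); "a total of approximately 160 subjects (80 per treatment) will be randomized".
- Protocol 10.3.1: "Non-inferiority will be concluded in each case if the upper bound of the 95.4% confidence interval" for tNPWT minus PICO is below 12.5. That is (1 − 0.954)/2 = 0.023 one-sided, z = 1.995.

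**Inputs assumed**

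- The share f of the final difference that drop-outs carry. The documents give neither the timing of drop-out nor the shape of healing, so f is varied from 0 to 0.875; f = 1 means no bias.
- Drop-out unrelated to outcome, and all 160 randomized subjects in the FAS.
- Area reduction counted as positive, as the decision rule requires. The 9.4 formula gives reductions a negative sign, which is a separate matter.

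**The plan's own figure.** A fixed design needs 2 × (1.960 + 0.842)² × 24.5²/12.5² = 60.3, so 61 per arm or 122 in all. Adding an interim at half the information, with efficacy bound 2.963, futility bound 0.559 counted as a loss of power and final bound 1.969, gives 80.2% power at 128 (79.6% at 126). Then 128/0.8 = 160. The stated 128 and 160 are reproduced.

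**FAS, equal drop-out, true difference at the margin.**

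SE = 24.5 × √(2/80) = 3.874.

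Expected difference D = 12.5 × (0.8 + 0.2f).

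False-positive rate = Φ(−1.995 + (12.5 − D)/SE), ignoring the interim look.

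| f | D | False-positive rate | Ratio to 2.3% |
|---|---|---|---|
| 0 | 10.0 | 8.9% | 3.8 |
| 0.25 | 10.6 | 6.5% | 2.8 |
| 0.5 | 11.25 | 4.7% | 2.05 |
| 0.66 | 11.65 | 3.8% | 1.6 |
| 0.75 | 11.9 | 3.3% | 1.4 |
| 0.875 | 12.2 | 2.8% | 1.2 |
| 1 | 12.5 | 2.3% | 1.0 |

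f = 0.5 corresponds to drop-out spread evenly over 12 weeks with linear healing. f = 0.66 corresponds to even drop-out with exponential healing to 60% and 47.5%. The rates are −ln(0.4) = 0.916 and −ln(0.525) = 0.644, the time-averaged difference is 100 × (0.475/0.644 − 0.6/0.916) = 8.2, and 8.2/12.5 = 0.66. With SD 21 and f = 0.5 the rate is 5.3%.

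A simulation (40,000 trials per scenario, weekly visits, unadjusted comparison) includes the extra spread that LOCF adds. It gives 4.2% to 4.5% for linear and 3.5% to 3.7% for exponential healing.

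**FAS, unequal drop-out** (f = 0.5, true means 60 and 47.5):

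- 15% tNPWT, 25% PICO: 60 × 0.925 − 47.5 × 0.875 = 55.5 − 41.6 = 13.9; rate 0.9%.
- 25% tNPWT, 15% PICO: 60 × 0.875 − 47.5 × 0.925 = 52.5 − 43.9 = 8.6; rate 16.4%.

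**Per Protocol.** Of the 20% who drop out, about a quarter (5%) leave late enough to stay in, carrying on average 0.875 of the final difference. D = 12.5 × (0.8 + 0.05 × 0.875)/0.85 = 12.4 and the rate is 2.4%. Simulation gives 2.3% to 2.5%.

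**The case against.** The strongest reply is that no error in the trial's main claim is shown. The primary test is Per Protocol, where the rate hardly moves. Because superiority needs non-inferiority in both sets, the joint error cannot exceed the Per Protocol error, whatever LOCF does to the FAS. This stands, and it limits the harm to the quality of the cross-check. It rests on drop-out being unrelated to outcome; the calculation does not cover selection caused by removing early discontinuers.

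The direction is not fixed either. Protocol 9.2 requires stopping study treatment for an area increase of at least 75% or a non-responding infection, and subjects who discontinue the study early should complete Visit 14, where an open ulcer is measured. LOCF can then carry a poor value forward, and if PICO were worse and had more such stops, it would widen the difference. This also stands. It is a further reason for a sensitivity analysis, since none of those planned for this endpoint would show the effect of an imbalance in an open-label trial.

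The planned comparison of Per Protocol with FAS is a partial check, since Per Protocol drops most early carried values. But it removes those subjects rather than varying what is assumed about them.

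The remedy has complications: forward covariate selection, a permutation fallback, many values at complete closure, and a target that becomes the outcome had the subject continued. These call for a few more lines of specification and do not defeat the point.

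A reader might also infer that LOCF reaches completers with open ulcers, because Protocol 9.1.5 has them skip the Visit 13 procedures. But they complete the Visit 14 procedures instead, which include measurement, and SAP 2.2 lists measurement through Visit 13. The documents do not establish that reading and it is not counted here.

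**Conclusion.** The point holds as a weakness of the FAS analysis. LOCF is the sole rule for open ulcers with a missing Visit 13 area, depth or volume, and nothing tests its influence. With 20% drop-out in each arm and a deficit of 12.5 that grows over time, the FAS false-positive rate for area goes from 2.3% to about 4.7% (half the final difference carried) or 3.8% (two thirds carried), within a range of about 3% to 9%.

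A reader might infer that the planned 20% drop-out by itself doubles the trial's false-positive rate. The documents do not support that. They give no drop-out timing, split by arm or healing curve; doubling is one scenario, and a modest imbalance moves the rate anywhere from 0.9% to 16.4%. Nor does the result carry over to the primary Per Protocol test, which stays at 2.3% to 2.5% under outcome-independent drop-out. The change is worth making because it is cheap, not because the primary claim is shown to be invalid.

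**What to change.** In SAP 2.3.5 and 4.9 to 4.10, prespecify for the FAS, for area, depth and volume:

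- Multiple imputation by arm from the weekly measurements already collected, with closed ulcers kept at 0. Use the initial covariate model, so that no selection across imputed datasets is needed. State that the target is the outcome had the subject continued, and whether the permutation fallback applies to imputed data.
- A delta-shift (tipping-point) analysis that worsens the imputed PICO values step by step until non-inferiority is lost, reporting the shift at which that happens.
- LOCF kept as a sensitivity analysis.

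If the imputation assumptions hold, drop-outs carry the full expected difference (f = 1) and the FAS rate returns to 2.3%. The cost is SAP text, programming and a slightly wider confidence interval. No new data are needed.
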